### 9.3 Vital Signs

Summary statistics for vital signs will be provided. For the double-blind treatment period, vital signs, change from baseline will be summarized for the Safety Sample by treatment group.

Potentially clinically relevant vital signs measurements identified in the double-blind treatment period for the Safety Sample will be summarized by treatment group. Criteria for identifying vital signs of potential clinical relevance are provided in [Appendix 1](#). All potentially clinically relevant events or changes will be listed and included in summary tables.

### 9.4 12-Lead ECG

Summary statistics and incidence of potentially clinically relevant changes will be provided for ECG parameters.

For the analysis of QT and QTc, data from three consecutive complexes (representing three consecutive heart beats) will be measured to determine average values. The following QT corrections will be used for reporting purposes in the clinical study report:

- 1) QTcB is the length of the QT interval corrected for heart rate by the Bazett formula:  

$$QTcB = QT / (RR)^{0.5}$$
 and
- 2) QTcF is the length of the QT interval corrected for heart rate by the Fridericia formula:  

$$QTcF = QT / (RR)^{0.33}$$
- 3) QTcN is the length of the QT interval corrected for heart rate by the FDA Neuropharm Division formula:  $QTcN = QT / (RR)^{0.37}$

Potentially clinically relevant changes in the 12-lead ECG identified in the double-blind treatment period for the Safety Sample will be listed and summarized by treatment group. Criteria for identifying ECG measurements of potential clinical relevance are provided in [Appendix 3](#).

Categorical changes in ECG parameters during the double-blind treatment period will be summarized based on the following criteria:

Categorical Change Criteria in QT/QTc Parameters		
Classification	Category	Criteria
QT	New Onset ( $> 450$ Msec)	New onset ( $> 450$ msec) in QT means a subject who attains a value $> 450$ msec during treatment period but not at baseline.
QTc *	New Onset ( $\geq 450$ Msec for men and $\geq 470$ Msec for women)	New onset ( $\geq 450$ Msec for men and $\geq 470$ Msec for women) in QTc means a subject who attains a

SAP 331-201-00080

Categorical Change Criteria in QT/QTc Parameters		
Classification	Category	Criteria
	for women)	value $\geq$ 450 Msec for men or $\geq$ 470 Msec for women during treatment period but not at baseline.
	New Onset ( $\geq$ 450 Msec for men and $\geq$ 470 Msec for women) And > 10% Increase	New onset ( $\geq$ 450 Msec for men and $\geq$ 470 Msec for women) and > 10% increase in QTc means a subject who attains a value $\geq$ 450 Msec for men or $\geq$ 470 Msec for women, and > 10% increase during treatment period but not at baseline
	New Onset (> 500 Msec)	New onset (> 500 msec) in QTc means a subject who attains a value > 500 msec during treatment period but not at baseline.
	Increase 30 - 60 Msec	Increase from baseline value > 30 and $\leq$ 60 msec in QTc
	Increase > 60 Msec	Increase from baseline value > 60 msec in QTc

\* QTc categorical change criteria apply to QTcB, QTcF and QTcN.

## 9.5 Physical Examinations

By-patient listings will be provided for physical examination.

### 9.5.1 Body Weight, Waist Circumference and BMI

Analyses of body weight, waist circumference and BMI will be performed for the Safety Sample. The mean change from baseline-to Day 21 (OC) and last visit in the double-blind treatment period in body weight will be tabulated and analyzed using ANCOVA. The ANCOVA models for both the OC and last visit analyses will include the baseline as a covariate and the treatment group as fixed effect.

[figure not shown]
Percentages of patients showing significant weight gain ( $\geq$  7 % increase in weight), as well as percentages of patients showing significant weight loss ( $\geq$  7 % decrease in weight) from baseline to Day 21 (OC and LOCF) will be analyzed using CMH General Association Test.

Body mass index is defined as weight in kilograms divided by the square of height in meters.

## 9.6 CCI

[REDACTED]

SAP 331-201-00080

### 9.7 Suicidality Data

Suicidality will be monitored during the study using the C-SSRS and will be summarized as number and percentage of subjects reporting any suicidal behavior, ideation, behavior by type (4 types), ideation by type (5 types) and treatment emergent suicidal behavior and ideation. Summary will be provided for the double-blind treatment period.

Suicidality is defined as report of at least one occurrence of any type of suicidal ideation or at least one occurrence of any type of suicidal behavior during assessment period (count each person only once).

Treatment emergent suicidal behavior and ideation is summarized by four types: Emergence of suicidal ideation, Emergence of serious suicidal ideation, Worsening of suicidal ideation, Emergence of suicidal behavior.

Emergence of suicidal behavior/ideation is defined as report of any type of suicidal behavior/ideation during treatment when there was no baseline suicidal behavior/ideation.

Emergence of serious suicidal ideation is defined as observation of suicidal ideation severity rating of 4 or 5 during treatment when there was no baseline suicidal ideation.

Worsening of suicidal ideation is defined as a suicidal ideation severity rating that is more severe than it was at baseline.

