12.	Subjects with serum concentrations of lithium \geq 0.6 mmol/L, serum concentrations of valproate \geq 50 μ g/mL, or serum concentrations of carbamazepine \geq 4 μ g/mL (if any of these parameters are outside of the listed exclusionary range, they may be reassessed prior to randomization, if necessary).
	Medical History and Concurrent Diseases
13.	Subjects who have a current diagnosis or history of substance or alcohol use disorder (excluding nicotine) (DSM-5 criteria) 120 days prior to the screening visit.
14.	Subjects who answer “Yes” on the C-SSRS Suicidal Ideation Item 4 (Active Suicidal Ideation with Some Intent to Act, Without Specific Plan) and whose most recent episode meeting criteria for this C-SSRS Item 4 occurred within the last 6 months, OR Subjects who answer “Yes” on the C-SSRS Suicidal Ideation Item 5 (Active Suicidal Ideation with Specific Plan and Intent) and whose most recent episode meeting criteria for this C-SSRS Item 5 occurred within the last 6 months OR Subjects who answer “Yes” on any of the 5 C-SSRS Suicidal Behavior Items (actual attempt, interrupted attempt, aborted attempt, preparatory acts, or behavior) and whose most recent episode meeting criteria for any of these 5 C-SSRS Suicidal Behavior Items occurred within the last 2 years, OR Subjects who, in the opinion of the investigator, present a serious risk of suicide or homicide.

Protocol 331-201-00080

Table 3.4.3-1 Exclusion Criteria

15.	Subjects with hypothyroidism or hyperthyroidism (unless condition has been stabilized with medications for at least the past 90 days) or an abnormal result for free T ₄ at screening.

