^oThe “Baseline/Screening” C-SSRS form will be completed for all subjects at screening to determine eligibility and the “Since Last Visit” C-SSRS form will be completed at the baseline visit to assure that the subject continued to qualify for the trial. Any subject with suicidal ideation within the last 6 months, suicidal behaviors within the last 2 years, or who in the clinical judgment of the investigator presents a serious risk of suicide should be excluded from the trial (see [Table 3.4.3-1](#)). The “Since Last Visit” C-SSRS form will be completed at all visits after the baseline visit.

^pAdverse events will be recorded starting after the subject signs the ICF.

^qCC1

^rSite staff will provide IMP to hospitalized subjects daily from assigned blister cards. If a subject is discharged at Day 14, the site should counsel the subject on the importance of taking IMP as directed.

Protocol 331-201-00080

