3.7.1.2 Baseline (Day 1)

If the subject continues to be eligible for the trial after the screening period, the following procedures will be performed:

- An assessment of all inclusion and exclusion criteria will be made to confirm the subject's eligibility for the trial.
- A qualified and certified rater will administer the YMRS, CGI-BP, **CCI** [REDACTED]
[REDACTED] [REDACTED]
- The investigator (or qualified designee) who is adequately trained will complete the "Baseline/Screening" C-SSRS form.
- Vital sign measurements (body temperature, blood pressure, and heart rate) will be recorded. Blood pressure and heart rate are to be measured in the following order: supine and standing after the subject has been in each position at least 3 minutes. See [Table 3.4.3-1](#) for exclusions based on outcome of screening vital sign measurements.
- A standard 12-lead ECG will be performed after the subject has been supine and at rest for at least 5 minutes. See [Table 3.4.3-1](#) for exclusions based on ECG results.
- Adverse events and concomitant medications will be recorded.

Protocol 331-201-00080

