3.7.3.5.4 Columbia-Suicide Severity Rating Scale

Suicidality will be monitored during the trial using the C-SSRS. This trial will use the “Baseline/Screening” and “Since Last Visit” versions of the scale. The “Baseline/Screening” version, which assesses the lifetime experience of the subject with suicide events and suicidal ideation and the occurrence of suicide events or ideation within a specified time period prior to entry into the trial, will be completed for all subjects at screening to determine eligibility. Any subject with active suicidal ideation within the last 6 months, suicidal behaviors within the last 2 years, or who in the clinical judgment of the investigator presents a serious risk of suicide should be excluded from the trial (Table 3.4.3-1). The “Since Last Visit” C-SSRS form will also be completed at all visits after screening. Copies of the C-SSRS forms are provided in [Appendix 13](#) and [Appendix 14](#).

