## 9 Safety Analysis

Standard safety variables to be analyzed include Adverse Events (AEs), clinical laboratory tests, vital signs, body weight, waist circumference, BMI, 12-lead electrocardiograms (ECGs), and physical examinations. CCI

and Columbia-Suicide Severity Rating Scale (C-SSRS).

SAP 331-201-00080

Safety analysis will be conducted based on the Safety Sample unless indicated otherwise. In general, baseline of a safety variable is defined as the last observation of the variable before taking the first dose of IMP, unless specified otherwise. Prospectively defined criteria will be used to identify potentially clinically relevant abnormal values for clinical laboratory tests, vital signs, ECGs, and body weight.

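### SAP 9.7 has no treatment-emergent row that isolates new serious suicidal ideation in subjects who start with milder ideation, and the documents disagree on the Day 1 C-SSRS form and the ideation exclusion that decide who those subjects are

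*SAP*

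**What the plan says.** SAP 9.7 summarises C-SSRS data for the double-blind period in two ways. One is without regard to baseline, including "ideation by type (5 types) and treatment emergent suicidal behavior and ideation", where the by-type part is a simple count of each ideation type. The other is a set of four treatment-emergent categories:

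- emergence of ideation, which requires no ideation at baseline;
- emergence of serious ideation, a "severity rating of 4 or 5 during treatment when there was no baseline suicidal ideation";
- worsening: "Worsening of suicidal ideation is defined as a suicidal ideation severity rating that is more severe than it was at baseline";
- emergence of behavior, which requires no behavior at baseline.

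Section 9.7 names no form or recall period for baseline. The general rule in SAP 9 is that "baseline of a safety variable is defined as the last observation of the variable before taking the first dose of IMP".

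The protocol and SAP differ on the Day 1 form. Footnote o of Table 3.7-1 names the Since Last Visit version and says that this "C-SSRS form will be completed at the baseline visit to assure that the subject continued to qualify for the trial". Protocol 3.7.3.5.4 and SAP 10.3.8 also assign Since Last Visit to every visit after screening, which includes Day 1. Protocol 3.7.1.2 instead says that on Day 1 the rater "will complete the 'Baseline/Screening' C-SSRS form". According to protocol 3.7.3.5.4, that version "assesses the lifetime experience of the subject with suicide events and suicidal ideation". Appendix 13 shows that it also has a past-6-month ideation column.

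The ideation exclusion is worded in three ways. Exclusion 14 in Table 3.4.3-1 bars subjects who endorse Item 4 and "whose most recent episode meeting criteria for this C-SSRS Item 4 occurred within the last 6 months", with a matching clause for Item 5. It does not list Items 1 to 3. Footnote o bars any suicidal ideation in the last 6 months. Protocol 3.7.3.5.4 and SAP 10.3.8 bar active suicidal ideation in that period.

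**The concern.** A change from passive or non-specific thoughts to ideation with intent or a plan is the kind of event a treatment-emergent suicidality table should show. This matters in a manic population that admits mixed features. As defined, the serious-emergence row shows such a change only in subjects who start from nothing. In subjects who start at 1 to 3 it is merged with one-step mild shifts.

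Whether such subjects exist depends on which exclusion wording a site applied. Their recorded baseline depends on which form was completed on Day 1. Two sites that each followed a current instruction could classify the same history differently, for ideation and for behavior.

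**Working it through.** There is no document figure to reproduce, so the check applies the SAP 9.7 definitions to every possible shift. No ideation is written as 0, and the items as 1 to 5.

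**Shifts into 4–5 on treatment, with Since Last Visit as the Day 1 form**

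| Exclusion wording | Eligible baseline | Shifts into 4–5 | In serious-emergence row | Outside it |
|---|---|---|---|---|
| Items 4–5 barred (Table 3.4.3-1) | 0, 1, 2, 3 | 4 × 2 = 8 | 2 (0→4, 0→5) | 6 |
| Active ideation barred (protocol 3.7.3.5.4, SAP 10.3.8) | 0, 1 | 2 × 2 = 4 | 2 | 2 |
| Any ideation barred (footnote o) | 0 | 1 × 2 = 2 | 2 | 0 |

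The second line reads active as Items 2 to 5, because Appendix 13 already labels Item 2 as active and describes Item 1 only as a wish to be dead.

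**Where the six shifts go under Table 3.4.3-1.** They are 1→4, 1→5, 2→4, 2→5, 3→4 and 3→5. None is in either ideation-emergence row, since both require no baseline ideation. All six meet the worsening definition. From baseline 1–3 that row holds 4 shifts from 1 (to 2, 3, 4, 5), 3 from 2 and 2 from 3: 4 + 3 + 2 = 9. Six of these end at 4–5 and three (1→2, 1→3, 2→3) do not. Read literally, with no ideation scored as 0, the row also takes 0→1 to 0→5, giving 9 + 5 = 14.

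**If lifetime recall became the baseline.** The Item 4 and 5 clauses of exclusion 14 do not bar ideation of 4–5 that was last present more than 6 months ago. A lifetime baseline of 4 or 5 against an on-treatment 4 or 5 gives 2 × 2 = 4 pairings. Only 4→5 is worsening. The pairings 4→4, 5→4 and 5→5 fall in no emergent row and appear only in the by-type counts.

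Behavior works the same way. Exclusion 14 bars behavior in the last 2 years, so an older attempt could count as lifetime baseline behavior. A new on-treatment attempt would then not be emergence, and there is no worsening row for behavior.

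**The case against.** The strongest reply is that SAP 9.7 nearly provides the count already. Under exclusion 14 with Since Last Visit on Day 1, no eligible subject has a baseline of 4–5. Every on-treatment 4 or 5 is then new, and subjects with any 4 or 5 minus the serious-emergence row are exactly the missing group. This is right in principle. But types 4 and 5 are tabulated separately, one subject can be in both, and 9.7 plans no combined count. The subtraction also fails if any baseline of 4–5 is recorded through lifetime recall.

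Second, SAP 9 and 10.3.8 read together imply that the Day 1 Since Last Visit form is the baseline, so the outlier is one bullet in protocol 3.7.1.2. That holds for the analysis intent. It does not govern what a site following that bullet would collect.

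Third, the lifetime case needs several things at once: a site using the other form, a programmer taking the lifetime column rather than the 6-month one, old serious ideation that the investigator did not judge a serious risk, and a 4–5 rating on treatment. It is remote, and nothing in the SAP selects lifetime recall.

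Fourth, footnote o and 3.7.3.5.4 cite Table 3.4.3-1 and may be loose summaries of it. Each is nonetheless broader than the table.

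Finally, the SAP's list of summary tables is redacted, so a planned shift table cannot be ruled out. The point is confined to the text of 9.7. These replies reduce the weight of the point but do not remove it.

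**Conclusion.** The concern holds and should be addressed. No event is lost from all summaries, but no treatment-emergent row identifies a move from 1–3 to 4–5 as new serious ideation. Depending on the exclusion wording, 6, 2 or 0 shift types are affected. These are counts of possible shifts, not proportions of subjects. The documents give no ideation rates, so the number of subjects is unknown and may be near zero.

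The two conflicts, over the Day 1 form and the ideation exclusion, are in current text and not only in the amendment log. The shift counts assume that a Day 1 Since Last Visit rating sets baseline and that active ideation means Items 2 to 5. The summaries are descriptive and the primary efficacy analysis is unaffected.

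**What to change.** - **SAP 9.7:** define emergence of serious ideation, or add a row for it, as an on-treatment rating of 4 or 5 with a baseline rating of 0 to 3. Under Table 3.4.3-1 this covers all 8 shift types instead of 2.
- **SAP 9.7:** add one sentence stating which C-SSRS form and recall period define baseline for ideation and for behavior.
- **Protocol 3.7.1.2:** bring the Day 1 form into line with footnote o, protocol 3.7.3.5.4 and SAP 10.3.8.
- **Ideation exclusion:** reconcile the wording in Table 3.4.3-1, footnote o, protocol 3.7.3.5.4 and SAP 10.3.8 so that sites apply one rule. Which rule is a clinical decision for the sponsor, and this review does not choose it.

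The cost is one definition or table row, one sentence and some protocol wording. No new data are needed.

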### 9.8 Concomitant Medications

Number and proportion of patients taking concomitant medications prior to study therapy, during the double-blind treatment period, and after study therapy are tabulated by drug classification using the WHO drug dictionary.

### 9.9 Extent of Exposure

The start date of double-blind study therapy - brexpiprazole or placebo - will be the first day of double-blind dosing. The number and percentage of patients who receive double-blind study medication, will be presented by week and by treatment group. Each dosing week will

SAP 331-201-00080

be based on the actual week; i.e., Day 1-7 in Week 1, Day 8-14 in Week 2, etc. This summary will be performed on the Safety Sample.

The mean daily dosage will be summarized by week and treatment group using descriptive statistics. The mean daily dosage per patient per week will be determined for each week of the study. This will be calculated by dividing the sum of individual total doses by the number of days in the week interval. The summary will contain for each treatment group the number of patients receiving double-blind study medication, and the mean and range of the mean daily dose for each week.

## 10 Conventions

### 10.1 Study Visit Windows

Study visit windows will be used to map visits using study day intervals. Observations at each scheduled visit and Early Termination will be assigned to Day 4, Day 7, Day 14 and Day 21 visits based on their visit windows as shown in [Table 10.1A](#). This visit window convention applies to tables and listings for all efficacy and safety scales (YMRS, CGI-BP, [CCI](#) [REDACTED] [REDACTED]). This derived study window variable will be named as DAY and will be footnoted. In listings, it will be listed along with the CRF study visit.

[Table 10.1A](#) shows classifications for study day intervals in the double-blind period. The variable “target day” is defined using the number of days since the start of double-blind dosing. The first day of double-blind dosing is defined as “Day 1”.

[figure not shown]
If more than one observation falls within a particular study day interval, then the last observation within that interval is used. Evaluations occurring more than 7 days after the last double-blind dosing date will not be mapped into study visit windows, and will be excluded from the analysis.

**Table 10.1A: Study Day and Visit Windows**

Day	Target Day a	Study Day Interval a
4	4	2-5
7	7	6-10
14	14	11-17
21	21	18-24 b

a Relative to the first day of IMP in the double-blind treatment period.

SAP 331-201-00080

### 10.3 Scales: Rules for Scoring and Handling of Missing Data

#### 10.3.1 YMRS

The YMRS is utilized as the primary efficacy assessment of a subject's level of manic symptoms. The YMRS consists of 11 items: 1) elevated mood, 2) increased motor activity-energy, 3) sexual interest, 4) sleep, 5) irritability, 6) speech (rate and amount), 7) language-thought disorder, 8) content, 9) disruptive-aggressive behavior, 10) appearance, and 11) insight. Seven items are rated on a 0- to 4-scale, while four items (Items 5, 6, 8, and 9) are rated on a 0- to 8-scale with 0, 2, 4, 6, and 8 being the possible scores (twice the weight of the other items). For all items, 0 is the "best" rating and the highest score (4 or 8) is the 'worst' rating. The YMRS Total Score is the sum of ratings for all 11 items; therefore, possible total scores range from 0 to 60. The YMRS Total Score is set to be missing if less than 9 of the 11 items are recorded. If 10 of the 11 items are available and the item missing is from items 5, 6, 8 or 9, then the YMRS Total Score is the sum of scores for items 1 to 4, 7, 10 to 11 plus the mean of the recorded items from 5, 6, 8 and 9 times four. If 10 of the 11 items are available and the item missing is from items 1 to 4, 7, 10 to 11, then the YMRS Total Score is the sum of scores for items 5, 6, 8 and 9 plus the mean of the recorded items from 1 to 4, 7, 10 to 11

SAP 331-201-00080

times seven. If 9 of the 11 items are available and both missing items are from items 5, 6, 8 and 9, then the YMRS Total Score is set to be missing. If 9 of the 11 items are available and both missing items are from items 1 to 4, 7, 10 to 11, then the Total Score was the sum of scores for items 5, 6, 8 and 9 plus the mean of the recorded items from 1 to 4, 7, 10 to 11 times seven. If 9 of the 11 items are available and one of the missing items is from items 1 to 4, 7, 10 to 11, and one of the missing items is from items 5, 6, 8 and 9, then the YMRS Total Score is the mean of the recorded items from 5, 6, 8 and 9 times four, plus the mean of the recorded items from 1 to 4, 7, 10 to 11 times seven. All imputed scores are rounded to the first decimal place.

### 10.3.2 CGI-BP

The CGI-BP scale refers to the global impression of the subject with respect to bipolar disorder. The scale rates the subject's Severity of Illness (CGI-BP severity of illness: mania, depression, and overall bipolar illness) and based on a 7-point scale and rates the subject's Change from Baseline (CGI-BP Change from Baseline: mania, depression, and overall bipolar illness) based on a 7-point scale. CGI-BP severity of illness items are: 1 = normal, not at all ill, 2 = minimally ill, 3 = mildly ill, 4 = moderately ill, 5 = markedly ill, 6 = severely ill, 7 = very severely ill. CGI-BP Change from Baseline items are: 1 = very much improved, 2 = much improved, 3 = minimally improved, 4 = no change, 5 = minimally worse, 6 = much worse, 7 = very much worse. The CGI-BP Change from Baseline is not assessed at the baseline visit. At each visit other than baseline, the Change from Baseline will be judged with respect to subject's condition at baseline.

